1.5 Study Design

The study BCA-12 is a cross-sectional observational study.

1.6 Study Schedule

As soon as the study BCA-12 is approved by the local ethical committee of the Christian-Albrechts-University Kiel, the BfArm and the BfS the subject recruitment will start. The measurement period of subjects is estimated with one year. The measurement duration per subject is 2 days.

1.7 Requirements on study procedure

Please refer to chapter 2.7 Procedure in this document.

1.8 Requirements on study population

Only subjects who meet the following inclusion and exclusion criteria shall be included in the study BCA-12:

Inclusion criteria:

- male and female subjects older than 60 years,
- subjects need to be able to sign the informed consent form

Exclusion criteria:

- acute disease
- intake of diuretics
- wearing of support stockings
- edema diagnosed by inspection and palpation of lower limbs
- paralysis e.g. after a stroke
- neurodegenerative diseases e.g. ALS
- tumors in treatment
- amputation
- electronic implants e.g. pacemaker
- under the skin applied injection systems (e.g. insulin pumps or pain pumps)
- probands who cannot provide an ICF by themselves
- probands who might be dependent from the sponsor or the investigation site
- current alcohol abuse
- active prostheses
- electronic life-support systems, e.g. artificial heart, artificial lung
- portable electronic medical devices, e.g. ECG devices or infusion pumps
- metallic implants
- cochlea implants und heart valves prothesis (e.g. Starr-Edwards-Prothesis)
- vessel clips in the brain or medulla applied before 1995
- defeatable pumps
- catheter
- iron or metallic parts in the body (e.g. shard of metal)
- dental braces
- magnetic tooth implants
- not removeable piercings
- extensive tattoos

seca	Clinical Investigation Plan Inv. code: BCA-12 Doc. code: 25-02-02-456	Rev. date: 16-01-19 Revision: 1.4 Page: 15 of 32
-------------	---	--

1.9 Subject Discontinuation Criteria

All subjects have the right to withdraw consent without prejudice at any time during the study. If a subject withdraws consent, the investigator should make a reasonable effort to determine the cause for withdrawal of consent. For these subjects, as well as for subjects who require permanent discontinuation from examination with the medical device, the investigator should make a reasonable effort to complete all required study procedures. All information should be documented in the subject's source data documents and on the Case Report Form (CRF). A subject who discontinues treatment will not be replaced. The subject's participation in this study should be permanently discontinued as a result of:

- formal withdrawal of informed consent
- investigator concludes that it is in the subject's best interest to discontinue study procedures
- presence of other medical conditions that prohibit continuation of study procedures
- subject is willingly or inadvertently non-compliant to any of the CIP procedures in the opinion of the investigator

1.10 Study Discontinuation Criteria

Study is discontinued only if irreversible failure of devices for measurement of body composition cannot be compensated.

2. INVESTIGATIONAL DEVICES

The seca medical Body Composition Analyzer (mBCA) is mainly used in hospitals, medical practices and inpatient care facilities in accordance with national regulations.

The mBCA records weight, height and bioelectrical impedance measurements and automatically calculates parameters such as fat-free mass (FFM) which can be derived from them. The results are displayed in graphical form and assist the attending physician with the following medical issues:

- determining energy expenditure and energy reserves as a basis for nutritional advice
- assessing metabolic activity and the success of a training program, e.g. within the framework of rehabilitation or physiotherapy
- determining a patient's fluids status

The mBCA is not intended for use on children.

2.1 Model for standing bioimpedance measurement: mBCA 515

seca	Clinical Investigation Plan Inv. code: BCA-12 Doc. code: 25-02-02-456	Rev. date: 16-01-19 Revision: 1.4 Page: 16 of 32
-------------	---	--

Technical Data

General:

- Dimensions (W×H×D): 976 × 1,251 × 828 mm
- Display type: 8.4" touch-screen display, can be swiveled 180° to the left and right
- Power supply: Power adapter
- Voltage: 100 V – 240 V
- Interfaces: seca 360° wireless, USB 2.0, Ethernet
- Microsoft® Windows® compatible printer via seca 115 PC software

Bioelectrical Impedance Analysis:

- Measurement method: 8-point Bioelectrical Impedance Analysis
- Type of electrode: Stainless steel, three pairs of hand electrodes, two pairs of foot electrodes
- Measurement frequencies: 1; 1.5; 2; 3; 5; 7.5; 10; 15; 20; 30; 50; 75; 100; 150; 200; 300; 500; 750; 1,000 kHz
- Measurements: Impedance (Z), Resistance (R), Reactance (Xc), Phase angle (φ)
- Measurement range Impedance: 10 Ω to 1,000 Ω
- Measurement segments: Right arm, left arm, right leg, left leg, right half of body, left half of body, torso
- Measurement current: 100 µA
- Measurement time: max. 90 seconds for 19 frequencies

The seca mBCA 515 has an integrated calibrated scale with a maximum load of 300kg. More information about the technical data for the scale and technical modifications can be found at the instruction for use for doctors and assistants at chapter 13.

PC software seca analytics 115:

The device mBCA 515 does not have "on-board" subject or user management. To manage subject files and user accounts, the device must be connected to a PC on which the seca 115 PC software is installed. Subject files can be created directly on the device to manage measured results. The subject files are stored in the database of the seca analytics 115 PC software supplied.

Recording weight and height:

The device uses an electronic scale. Weight is recorded across 4 load cells. Height is recorded via wireless transmission from the seca 274 length measuring device.

Bioimpedance measurement:

Bioimpedance is measured according to the 8-point method. The flow of the low alternating current and the measurement of impedance are performed for each side of the body using a pair of foot electrodes and a pair of hand electrodes. The hand electrodes are attached at different heights so that persons with different heights can adopt the ideal position on the device for a bioimpedance measurement.

2.2 Model for standing bioimpedance measurement: mBCA 555

Figure 1: mBCA 555 (left: without display)

Technical Data

General:

- Dimensions (W×H×D): 840 × 1,280 × 655 mm
- Display type: 4,3 inch TFT touch screen with a 16:9 format, can be swiveled 180° to the left and right
- Power supply: Power adapter
- Voltage: 100 V – 240 V
- Interfaces: seca 360° wireless, WiFi, Ethernet
- Medical device class IIa

Bioelectrical Impedance Analysis:

- Measurement method: 8-point Bioelectrical Impedance Analysis
- Type of electrode: Stainless steel, four pairs of hand electrodes, two pairs of foot electrodes
- Measurement frequencies: 1, 2, 5, 10, 20, 50, 100, 200 and 500 kHz
- Measurements: Impedance (Z), Resistance (R), Reactance (Xc), Phase angle (ϕ)
- Measurement range Impedance: 10 Ω to 1,000 Ω
- Measurement segments: Right arm, left arm, right leg, left leg, right half of body, left half of body, torso
- Measurement current: 100 μ A
- Measurement time: 30 seconds

The seca mBCA 555 has an integrated calibrated scale with a maximum load of 300kg. More information about the mBCA 555 can be found in the investigator's brochure.

2.3 Model for supine bioimpedance measurement: mBCA 525

Technical data

General:

- Dimensions (W×H×D): 252 × 262 × 230 mm / 9.0 x 10,3 x 9,1 "
- Weight: 3 kg / 6,6 lbs
- Display type: 7" touch-screen display
- Power supply: Power adapter, rechargeable battery
- Voltage: 100 V – 240 V
- Power frequency: 50 Hz – 60 Hz
- Interfaces: WiFi, seca 360° wireless, USB 2.0, Ethernet
- Microsoft® Windows® compatible printer via seca 115 PC software

Device components:

The device consists of a monitor and a measuring mat. The monitor is for administering patient and user data and for preparing and evaluating bioimpedance measurements. The device is equipped with a touchscreen display. The monitor has a storage compartment with a magnetic catch for storing the measuring mat. The measuring mat is placed on the patient's legs for a bioimpedance measurement. Measured results are transmitted to the monitor unit by WiFi. The electrode cables of the measuring mat are equipped with connections for push-button electrodes.

Bioelectrical Impedance Analysis:

- Measurement method: 8-point Bioelectrical Impedance Analysis
- Type of electrode: adhesive electrodes (PVC free)
- Measurement frequencies: 1; 2; 5; 10; 20; 50; 100; 200; 500; kHz
- Measurements: Impedance (Z), Resistance (R), Reactance (Xc), Phase angle (φ)
- Measurement range Impedance: 10 Ω to 1,000 Ω
- Measurement segments: Right arm, left arm, right leg, left leg, right half of body, left half of body, torso
- Measurement current: 100 µA
- Measurement time: 30 seconds

Recording weight and height:

The subject's weight and height is recorded manually.

Bioimpedance measurement:

The bioimpedance measurement is carried out with the subject lying down, using the 8-point method. The electrode cables are connected to two pairs of electrodes for each half of the body. The electrodes are affixed to the patient's hands and feet.

Management of patient files:

Subject files can be created directly on the device to manage measured results. The subject files are stored in the patient database of the device or in the seca analytics 115 PC software.

Subject files can be managed and edited using the mBCA 525 or the seca 115 PC software.

[figure not shown]
The two devices mBCA 515 and 525 differ in two ways. One difference is the measurement position. The mBCA 515 measures the subject in standing position, while measurements with the mBCA 525 are conducted in supine position. Since fluids in the body shift, when the patient lies down, the measurements differ between these two positions. Another difference between the two devices is the placement of the electrodes. The mBCA 515 measures for example parts of the hands that are not included in measurements with the mBCA 525. These differences lead to different measurements too. To be able to distinguish these two effects in the analysis, an additional measurement with the mBCA 525 in standing position shall be made.

2.4 Reference Methods

The following reference methods are used to cross-validate the results of the mBCA 525 and 515:

Magnetic Resonance Imaging (MRI)

MRI is a special radiology technique designed to image internal structures of the body using magnetism, radio waves. MRI uses a tube scanner surrounded by a giant circular magnet. The patient is placed on a moveable bed that is inserted into the magnet. The magnet creates a strong magnetic field that aligns the protons of hydrogen atoms, which are then exposed to a beam of radio waves. This spins the various protons of the body, and they produce a faint signal that is detected by the receiver portion of the MRI scanner. A computer processes the receiver information and an image is produced. The image and resolution is quite detailed compared to other technology and can detect tiny changes of structures within the body, particularly in the soft tissue, brain and spinal cord, abdomen and joints. The whole-body scan takes about 15 minutes.

[figure not shown]
[figure not shown]

Magnetic Resonance Imaging: MAGNETOM manufactured by SIEMENS (left) and MRI scan (right)

In Body Composition, MRI is used as gold standard to calculate the volume of different body compartments as SMM or adipose tissue. Different body compartments are segmented manually by a trained observer based on grey level differences within the MRI scan. The measured area (cm^2) is then multiplied with the slice thickness to generate the tissue volume (cm^3). By further multiplication with the specific tissue density the mass of the body compartment is calculated.

Dual-Energy X-Ray Absorptiometry (DXA)

Dual-Energy X-Ray Absorptiometry commonly referred to as DEXA or DXA, is a technique originally developed for the determination of Bone Mineral content in the detection and treatment of osteoporosis.

Dual-Energy X-Ray Absorptiometry: Hologic Discovery A (left) and DXA scan (right)

More recently, application of the technique has been expanded to include the analysis of Fat Mass (FM) and Lean Soft Tissue (LST), in addition to Bone Mass (BM). DXA is a two compartment method, but estimations allow the calculation of three compartments (FM, LST and BM).

The radiation exposure of a DXA Scan is around 7 to 10 μ Sv and much lower than an x-ray scan of the chest with around 100 μ Sv.

[figure not shown]
Dilution methods (D₂O, NaBr)

To calculate TBW and ECW dilution methods are regarded as gold standard. These methods involve orally administering a defined amount of a tracer in accordance with the subject's weight and determining the dilution of the tracer in the plasma after a 4 hour equilibration phase. The stable isotope of Hydrogen Deuterium (D₂O) is used to determine TBW. The salt Sodium Bromide (NaBr) of which only very small amounts pass through the cell membrane is used to determine ECW.

A D₂O dose of 100 mg per kg body weight mixed with tap water is administered orally in the morning fasting and after a 2 hour fluid abstention. The distribution of the stable isotope in the TBW is completed after 4 hours. During this period, the subject remains fasting. Two venous blood samples of 10 ml whole blood are taken immediately before and four hours after taking D₂O. The plasma samples are analyzed using Fourier Transformation Spectroscopy, Isotopic Ratio Mass Spectrometry (IRMS) or Photospectrometry. Spectroscopy is used to comprise any measurement of a quantity as a function of either wavelength or frequency. Spectrometry is the spectroscopic technique used to assess the concentration or amount of a given chemical species such as atomic, molecular or ionic. In this case, the instrument that performs such measurements is a spectrometer, spectrophotometer, or spectrograph. Deuterium dilution is a reliable, unstressful method to determine TBW, which is also suitable for pregnant or breastfeeding women and children [2, 3]. This method is classified as accurate and safe for the patient, but not fast for the user.

Orally administered NaBr is resorbed quickly and completely and almost exclusively distributes in the extracellular compartment [4]. Blood samples of 10 ml are taken immediately before and 4 hours after oral application of 40 mg NaBr per kg body weight. The serum sample after ultrafiltration can be analyzed using Anion Exchange Chromatography and UV Detection at 200 nm according to Miller et al. 1989. Alternatively, the serum can be analyzed by X-Ray Fluorescence Spectroscopy (XRF). XRF is the emission of characteristic "secondary" or fluorescent X-rays from a material that has been excited by bombarding with high-energy X-rays or gamma rays [5]. In general, this analysis is performed without opening the vial, therefore preserving the full amount of specimen for the next analysis as D₂O. Historically, bromide salts were used as anticonvulsants and sedatives. The oral NaBr dose for measuring ECW is below the pharmacologically effective dose (more than 1 to 6 g per day), however. The No-Observed Effect Level (NOEL) for NaBr is 100 mg per kg per day and the Acceptable Daily Intake (ADI) for NaBr from food and drinking water is 1 mg per kg per day [6]. On 82 healthy subjects in an age range of 12 to 65 years (BMI of 15.3 to 48 kg/m²), no adverse reactions were observed after taking NaBr doses of 30-60 mg per kg per day [7]. The route of elimination is renal (half-life of 11 to 12 days). As dilution methods require a certain effort these techniques are used for scientific purposes only.

Air Displacement Plethysmography (ADP)

Air Displacement Plethysmography: BOD POD® device, manufactured by COSMED S.r.l., Rome, Italy (left) and measurement principle (right)

FM and FFM are measured using Air Displacement Plethysmography (ADP). ADP is performed by the BOD POD® device (Cosmed S.r.l., Rome, Italy). Participants wear tight-fitting underwear and a swim cap. Two repeated measurements of body volume are performed, averaged and corrected for predicted body surface area and thoracic gas volume using BOD POD® software (version 4.5.0). Percentage fat mass (FM) is calculated from body density using the equation by Siri et al. (Siri, W.E. Body composition from fluid spaces and density: Analysis of methods. 1961. Nutrition 1993, 9, 480–491). Fat free mass (FFM) is calculated as body weight minus FM.

2.5 mBCA Device Accountability

The mBCA 515 and 525 devices are delivered and installed by the sponsor. The responsible staff at the Clinical Investigation Site stores the product in a secure, limited access area under normal temperature and humidity conditions. After completion of the CI the devices are to be returned to the sponsor.

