Feet	
 Stand on device with bare feet Feet must be clean Heels on the rear foot electrodes Balls of feet on the front foot electrodes 									
Position	
 Upright position Knees slightly bent Do not move during the measurement 									
42. If the patient is in correct contact with an electrode pair, start the measurement with the PC software	investigator									
43. As soon as the measurement ends, the message "BIA measurement: OK" appears --> measurement must be saved manually	investigator									
mBCA 525 measurement in standing position		5								
44. keep subject standing	investigator									
45. start mBCA 525	investigator									
46. login as user "BCA-12"	investigator									
47. select subject file to be measured	investigator									
48. enter weight, height, PAL and waist circumference	investigator									
49. click on BIA tab	investigator									
50. follow instructions on the monitor screen	investigator									
51. save measurement data	investigator									
52. check in seca analytics 115 if measurement data was saved	investigator									
mBCA 525 measurement in lying position		15								
53. make sure subject lays down for 10 min.	investigator									
54. login as user "BCA-12"	investigator									
55. select subject file to be measured	investigator									
56. enter weight, height, PAL and waist circumference	investigator									
57. click on BIA tab	investigator									
58. follow instructions on the monitor screen	investigator									
59. save measurement data	investigator									
60. check in seca analytics 115 if measurement data was saved	investigator									

Examination schedule	responsible	time in minutes
blood drawing		25
61. take baseline blood sample (30ml)	investigator	
62. calculate NaBr and D2O amount based on body weight	investigator	
63. weigh D2O within a flask	investigator	
64. add NaBr to the fluid and solve the dry chemical within the fluid D2O	investigator	
65. ask subject to drink the solution quickly	investigator	
66. inform subject not to drink within the next 4 hours	investigator	
67. after 4h take the next blood sample (30ml)	investigator	
DXA measurement		30
68. accompany the subject to the clinic of radiology (UKSH, Kiel)	investigator	
69. starting QDR program on the DXA connected PC	investigator	
70. click on daily quality control tab	investigator	
71. measure the spine phantom for quality control	investigator	

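### Section 2.4 calls the NaBr dose lower than 1 to 6 g per day, but 40 mg/kg is 2.0 to 4.0 g at 50 to 100 kg; the dose needs a different justification and a kidney question before it

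*Combined protocol and SAP*

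**What the plan says.** Section 2.4, under the dilution methods, measures extracellular water (ECW) with an "oral application of 40 mg NaBr per kg body weight", with blood drawn before and 4 hours after. It mentions the former medical use of bromide and then reassures the reader: "The oral NaBr dose for measuring ECW is below the pharmacologically effective dose (more than 1 to 6 g per day), however".

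The same paragraph gives further support. It states that "The No-Observed Effect Level (NOEL) for NaBr is 100 mg per kg per day" and gives an acceptable daily intake of 1 mg/kg from food and drinking water. It then cites a series: "On 82 healthy subjects in an age range of 12 to 65 years", "no adverse reactions were observed after taking NaBr doses of 30-60 mg per kg per day". It adds that bromide leaves through the kidney with a half-life of 11 to 12 days, and closes: "As dilution methods require a certain effort these techniques are used for scientific purposes only".

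Section 1.8 admits people over 60. Its exclusions include acute disease, diuretic use and edema, but no kidney disease or kidney function item. The revision history explains this: revision 1.2, after ethics committee feedback, replaced a heart or kidney item with diuretic use so that medical pre-examinations were not needed. In section 2.8 eligibility is checked again at step 10, and NaBr enters as a step of its own, step 64: "add NaBr to the fluid and solve the dry chemical within the fluid D2O". Section 4.1.2 describes every examination as clinical routine and reports no further known risk from dilution.

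**The concern.** The quoted sentence is the plan's direct answer to the fact that bromide was once used as a drug. An ethics committee or investigator reads there why the dose is acceptable in older volunteers. If the stated comparison is false, the justification rests on a wrong figure, although a sound one stands in the same paragraph.

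Two related gaps concern the same dose. The plan states renal elimination, but nothing asks about the kidney before dosing. A person with known kidney insufficiency who takes no diuretic and has no edema or acute disease would receive the full amount. And 4.1.2 presents as routine a method that 2.4 reserves for research.

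The stake is the safety justification and the screening. The prediction equations are not affected.

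**Working it through.** **Inputs.** From section 2.4: 40 mg/kg, given once; effective dose more than 1 to 6 g per day; NOEL 100 mg/kg per day; tolerated doses 30 to 60 mg/kg per day in 82 healthy subjects aged 12 to 65; half-life *h* = 11 to 12 days. From section 3: N = 150, made up of 124 plus 26 aged 60 to 65. Assumed: body weights, because the plan gives no weight distribution.

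**1. Can the plan's comparison be reproduced?** Dose in grams = 0.040 × weight in kg.

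| Weight (kg) | Dose (g) |
|---|---|
| 25 | 1.0 |
| 50 | 2.0 |
| 70 | 2.8 |
| 100 | 4.0 |
| 150 | 6.0 |

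The limits are 1000/40 = 25 kg and 6000/40 = 150 kg. The claim holds against the upper end of the range for anyone under 150 kg, but the text puts the start of effectiveness just above 1 g. Against that end it fails for any adult weight. Staying under 1 g would need less than 1000/50 = 20 mg/kg at 50 kg, or less than 1000/100 = 10 mg/kg at 100 kg.

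**2. Does the dose have other support in the plan?**

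- Share of the NOEL: 40/100 = 0.4.
- Cited experience: 40 lies between 30 and 60 mg/kg.
- Single against sustained dosing: with first-order elimination and one dose a day, the steady-state load is the daily dose × 1/(1 − 2^(−1/h)). The factor is 16.4 for h = 11 and 17.8 for h = 12. Sustained use of 1 g per day therefore builds up to about 16 to 18 g, against 2 to 4 g from one study dose.

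The third comparison assumes that the quoted effective dose refers to sustained daily use. The plan gives it per day but does not say for how long. The first two do not need that assumption.

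**3. How far does the cited experience reach?** It ends at age 65. If the 124 are spread evenly over 60 to 80 and the 26 are aged 60 to 65, then 0.75 × 124 = 93 of 150 (62%) are over 65. If all 124 are over 65, the figure is 124 of 150 (83%). For most subjects the series is therefore an extrapolation.

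**4. What would a kidney question cost in ECW data?** The shares are assumed. Interval widening = √(150/n), with the residual spread taken as unchanged.

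| Report kidney insufficiency | ECW values lost | n | Widening |
|---|---|---|---|
| 2% | 3 | 147 | 1.010 |
| 5% | 8 (7.5 rounded) | 142 | 1.028 |
| 10% | 15 | 135 | 1.054 |

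**The case against.** The strongest defence is that the faulty sentence changes little. Dosing is set in mg/kg and does not depend on it. It compares one dose with a daily regimen, and by the plan's own half-life a sustained regimen loads the body far more. The NOEL and the tolerance data appear in the same paragraph. All of this stands. It supports the dose, but it does not make the sentence true.

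On the kidney, the sponsor can say that the absence is a documented choice made after ethics committee feedback. Diuretic use, edema and acute disease screen indirectly, the synopsis asks for six months of stable medication, and section 1.9 lets the investigator stop in the subject's interest. This also stands, so an exclusion with laboratory testing would go too far. A question by history needs no pre-examination and fits that choice.

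A reader might infer more than the documents support:

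- *That the dose is harmful.* Nothing shows this. Being 40 times the acceptable daily intake does not show it either, since that limit is stated for daily intake from food and drinking water.
- *That nobody sees the subject after dosing.* A 4-hour blood sample follows, DXA, ADP, MRI and handgrip are listed after it, and measurement takes 2 days.
- *That the age limit of the series is hidden.* Section 2.4 prints it. What is missing is a remark that this study goes beyond it.
- *That a 30-day telephone call is needed.* The 30-day text in section 5.3 concerns adverse events already open. Without a control group, later symptoms in people over 60 could not be attributed to bromide, and section 5.2 would require immediate notice of unrelated serious events.

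**Conclusion.** The point holds as a correction to the justification, together with one inexpensive precaution. On the plan's own figures the NaBr dose is not below the stated effective range; it lies within it from 25 to 150 kg. This is plain arithmetic, and only the choice of 50 to 100 kg as typical weights is assumed. The source of the 1 to 6 g figure was not available and was not checked.

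The dose remains defensible as a single administration at 0.4 of the NOEL, within the cited tolerated range, provided the text admits that the range was observed only up to age 65. The missing kidney question is a reasonable improvement, because the plan itself names renal elimination. It is not evidence that subjects are at risk. The conflict between 2.4 and 4.1.2 over routine and research use is a matter of wording. The whole point is one for the sponsor to consider; it does not bear on the analysis.

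**What to change.** 1. **Section 2.4.** Replace the sentence. Suggested text: *The single dose is 2.0 to 4.0 g at 50 to 100 kg. It lies numerically inside the daily range quoted for therapeutic use, but it is given once and is 0.4 of the NOEL. The cited tolerance series includes no subject over 65.*
2. **Section 4.1.2.** Describe dilution as a research procedure, in line with 2.4.
3. **Section 2.8, step 10.** Ask, by history only, about known kidney insufficiency. If yes, omit NaBr at step 64, give D2O as planned and keep the subject for all other methods. Report how many ECW values are missing for this reason.

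**Cost.** The change takes two wording edits, one question and one CRF line, submitted as an amendment under section 9.1. It needs no tests and no further visits. The loss of ECW values is selective: 3 to 15 of 150 under the assumed 2% to 10%, with intervals about 1% to 5% wider. The ECW equation would then apply to people without known kidney insufficiency, a population slightly different from that for total body water. There is no spare margin to absorb the loss, since the 124 come from the precision calculation for resistance and the 26 serve the age overlap. A history question will also miss kidney disease that has not been diagnosed.
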